APPENDIX 5. LIST OF TABLES, FIGURES AND LISTINGS

List of Tables

| Table | Table Title |
|-----------|--|
| Number | |
| 14.1.1.1 | Summary of Subject Disposition (Enrolled Population) |
| 14.1.1.2 | Summary of Reasons for Discontinuation (Safety Population) |
| 14.1.1.3 | Summary of Reasons for Screen or Run-in Failure (All Enrolled Population) |
| 14.1.1.4 | Summary of Inclusion, Exclusion and Induction Phase Criteria Deviations (Safety Population) |
| 14.1.1.5 | Summary of Important Protocol Deviations (Safety Population) |
| 14.1.1.6 | Summary of Important Protocol Deviations Leading to Exclusion to Treatment (Safety Population) |
| 14.1.1.7 | Summary of Important Protocol Deviations Related to COVID-19 Pandemic (Safety Population) |
| 14.1.1.8 | Summary of Visits Impacted by COVID-19 Pandemic (Safety Population) |
| 14.1.2.1 | Summary of Demographic Characteristics (Safety Population) |
| 14.1.2.2 | Summary of Asthma History and Baseline Disease Characteristics (Safety Population) |
| 14.1.2.3 | Summary of Asthma Exacerbation History (Safety Population) |
| 14.1.2.4 | Summary of Family History of Cardiovascular Risk Factors (Safety Population) |
| 14.1.2.5 | Summary of Medical Conditions (Safety Population) |
| 14.1.2.6 | Summary of Asthma Medications Taken by Treatment Period and Respiratory Medication Class |
| | (Safety Population) |
| 14.1.2.7 | Summary of Non-Asthma Concomitant Medications Taken During Treatment (Safety Population) |
| 14.1.2.8 | Summary of Screening, Run-in and Baseline Lung Function Results (Safety Population) |
| 14.1.3 | Summary of Treatment Exposure and Number of Study Drug Administration (Safety Population) |
| 14.2.1.1 | Analysis of Subject Achieved at least 50% Reduction in OCS Dose During Weeks 20-24 |
| 44.0.4.0 | Relative to Baseline, while Maintaining Asthma Control (Safety Population) |
| 14.2.1.2 | Summary of OCS Dose Categories During Weeks 20-24 (5 mg Cut-off) (Safety Population) |
| 14.2.1.3 | Summary of OCS Dose Category During Each Reporting Period (Safety Population) |
| 14.2.1.4 | Summary of Percent Change from Baseline OCS Dose Categories Relative to Baseline by Reporting Period (Safety Population) |
| 14.2.1.5 | Summary of OCS Dose (mg/day) and Change from Baseline During Each Reporting Period (Safety Population) |
| 14.2.1.6. | Summary of Median Percent OCS Dose (mg/day) Reduction During Weeks 20-24 While |
| | Maintaining Asthma Control (Safety Population) |
| 14.2.2.1 | Overview of Exacerbations (Safety Population) |
| 14.2.2.2 | Summary of Frequency of Clinically Significant Exacerbations (Safety Population) |
| 14.2.2.3 | Analysis of Rate of Clinically Significant Exacerbations (Safety Population) |
| 14.2.2.4 | Summary of Frequency of Exacerbations Requiring Hospitalization or Emergency |
| | Department Visits (Safety Population) |
| 14.2.2.5 | Analysis of Rate of Exacerbations Requiring Hospitalization or Emergency |
| 14.0.0.0 | Department Visits (Safety Population) |
| 14.2.2.6 | Summary of Frequency of Exacerbations Requiring Hospitalization (Safety Population) |
| 14.2.2.7 | Analysis of Rate of Exacerbations Requiring Hospitalization (Safety Population) |
| 14.2.3.1 | Analysis of Change from Baseline in Clinic Pre-Bronchodilator FEV1 by Visit (Safety Population) |
| 14.2.3.2 | Analysis of Change from Baseline in Clinic Post-Bronchodilator FEV1 by Visit (Safety Population) |
| 14.2.3.3 | Summary of Pre-Bronchodilator FEV1 (Safety Population) |
| 14.2.3.4 | Summary of Post-Bronchodilator FEV1 (Safety Population) |
| 14.2.4.1 | Analysis of Change from Baseline in Asthma Control Questionnaire (ACQ-5) Scores(Safety Population) |
| 14.2.4.2 | Summary of Asthma Control Questionnaire (ACQ-5) Scores (Safety Population) |
| 14.2.5.1 | Analysis of Change from Baseline in Morning Peak Expiratory Flow (L/min) by 4-Week (Safety Population) |
| 14.2.5.2 | Summary of Morning Peak Expiratory Flow (L/min) by 4-Week Reporting Period (Safety Population) |
| 14.2.6.1 | Summary of Clinician Rated Overall Evaluation of Response to Therapy (Safety Population) |

| 14.2.6.2 | Summary of Subject Rated Overall Evaluation of Response to Therapy (Safety Population) |
|-----------|--|
| 14.2.7 | Summary of Work Productivity and Activity Impairment Score Composite Scores (WPAI:GH) |
| | (Safety Population) |
| 14.2.8.1 | Analysis of Change from Baseline in Salbutamol Use (occasions/day) by 4-Week Period (Safety Population) |
| 14.2.8.2 | Summary of Daily Salbutamol Use (occasions/day) by 4-Week Period (Safety Population) |
| 14.2.8.3 | Analysis of change from baseline Daily Asthma Symptom Scores by 4-Week Period (Safety Population) |
| 14.2.8.4 | Summary of Daily Asthma Symptom Scores by 4-Week Period (Safety Population) |
| 14.2.8.5 | Analysis of Change From Baseline Awakening at Night Due to Asthma Symptoms Requiring Rescue Medication Use by 4-Week Period (Safety Population) |
| 14.2.8.6 | Summary of Awakening at Night Due to Asthma Symptoms Requiring Rescue Medication Use by 4-Week Period (Safety Population) |
| 14.2.8.7 | Summary of Nasal Polyps Shifts from Baseline to Week 24/EOS (Safety Population) |
| 14.2.8.8 | Analysis of Ratio to Baseline in Blood Eosinophils (Unit) at Week 24 (Safety Population) |
| 14.2.8.9 | Summary of Blood Eosinophils (Unit) (Safety Population) |
| 14.2.8.10 | Analysis of Ratio to Baseline in Serum IgE (Total) Level (Unit) at Week 24 (Safety Population) |
| 14.2.8.11 | Summary of Total IgE Level (Unit) (Safety Population) |
| 14.3.1.1 | Overview of All Adverse Events (Safety Population) |
| 14.3.1.2 | Summary of Adverse Events by Treatment Period (On and Post-Treatment), System Organ Class And Preferred Term (Safety Population) |
| 14.3.1.3 | Summary of Common (>=3%) Non-serious Adverse Events by Treatment Period (On and Post-Treatment), System Organ Class and Preferred Term (Safety Population) |
| 14.3.1.4 | Summary of Adverse Events Occurred on the Day of Dosing by System Organ Class and Preferred Term (Safety Population) |
| 14.3.1.5 | Summary of On-treatment Drug-Related Adverse Events by System Organ Class and Preferred Term (Safety Population) |
| 14.3.1.6 | Summary of On-treatment Adverse Events Leading to Premature Discontinuation of Study by System Organ Class and Preferred Term (Safety Population) |
| 14.3.2.1 | Summary of Serious Adverse Events by Treatment Period (Pre, On and Post-Treatment), System Organ Class and Preferred Term (Safety Population) |
| 14.3.2.2 | Summary of Non-Fatal Serious Adverse Events by Treatment Period (Pre, On and Post-Treatment), System Organ Class and Preferred Term (Safety Population) |
| 14.3.2.3 | Summary of All Fatal Adverse Events by Treatment Period (On and Post-treatment), System Organ Class and Preferred Term (Safety Population) |
| 14.3.2.4 | Summary of On-Treatment Serious Adverse Events and Adverse Events of Special Interest by System Organ Class and Preferred Term (Safety Population) |
| 14.3.3.1 | Summary of On-treatment Adverse Events of Special Interest: Events Reported by the Investigator as Systemic Reactions - Allergic (Type I Hypersensitivity) (Safety Population) |
| 14.3.3.2 | Summary of On-Treatment Adverse Events of Special Interest: Events Reported by the Investigator as Systemic Reactions – Other Reactions (Safety Population) |
| 14.3.3.3 | Summary of On-Treatment Adverse Events of Special Interest: Systemic Reactions Reported by the Investigator as Meeting the Criteria for Anaphylaxis (Safety Population) |
| 14.3.3.4 | Summary of On-Treatment Adverse Events of Special Interest: Events Reported by the Investigator as Local Injection Site Reactions (Safety Population) |
| 14.3.3.5 | Summary of On-Treatment Adverse Events of Special Interest: Potential Opportunistic Infections (Safety Population) |
| 14.3.3.6 | Summary of On-Treatment Adverse Events of Special Interest: Malignancies (Safety Population) |
| 14.3.3.7 | Summary of On-Treatment Adverse Events of Special Interest: Serious Cardiac, Vascular and Thromboembolic Adverse Events (Safety Population) |
| 14.3.3.8 | Summary of On-Treatment Adverse Events of Special Interest: Serious Ischemic Adverse Events (Safety Population) |
| 14.3.3.9 | Summary of On-Treatment COVID-19 Assessments for Subjects with Suspected, Probable or Confirmed COVID-19 Case Diagnosis by System Organ Class and Preferred Term (Safety Population) |
| 14.3.3.10 | Summary of On-Treatment All Cardiovascular Events Reported by the Investigator (Safety Population) |
| 14.3.4.1 | Summary of Hematology Parameters (Safety Population) |

| 14.3.4.2 | Summary of Clinical Chemistry Parameters (Safety Population) | |
|----------|---|--|
| 14.3.4.3 | Summary of Shifts from Baseline to Week 24/EOS in Hematology Parameters (Safety Population) | |
| 14.3.4.4 | Summary of Shifts from Baseline to Week 24/EOS in chemistry Parameters (Safety Population) | |
| 14.3.5.1 | Summary of Binding Anti-Drug Antibody (ADA) Assay: Highest Confirmatory Result (Safety | |
| | Population) | |
| 14.3.5.2 | Summary of Neutralizing Antibody Assay: Highest Result (Safety Population) | |
| 14.3.5.3 | Summary of Binding Anti-Drug Antibody (ADA) Assay: Highest Treatment Emergent Confirmatory | |
| | Result (Safety Population) | |
| 14.3.6 | Summary of Vital Signs Parameter Results (Safety Population) | |
| 14.3.7.1 | Summary of ECG Parameter Results (Safety Population) | |
| 14.3.7.2 | Summary of ECG Findings (Safety Population) | |
| 14.3.7.3 | Summary of Abnormal Values for ECG Parameters According to Range Criteria (Safety | |
| | Population) | |
| 14.3.8.1 | Summary of Steroid Toxicity and Withdrawal (Safety Population) | |
| 14.3.8.2 | Summary of Steroid Toxicity and Withdrawal: Serum Glucose and Body Weight (Safety | |
| | Population) | |

List of Figures

| Figure Number | Figure Title |
|------------------|--|
| 14.4.1.1 | Time to Discontinuation of Study Treatment (Safety Population) |
| 14.4.1.2 | Histogram of OCS Doses Received by 4-Weeks Reporting Period (Safety Population) |
| 14.4.1.3 | Change from Baseline in Pre-Bronchodilator FEV1(mL) values (Safety Population) |
| 14.4.1.4 | Change from Baseline Asthma Control Questionnaire (ACQ-5) Scores by 4-Weeks Reporting Period (Safety Population) |
| 14.4.1.5 | Change from Baseline in Morning PEF by 4-Weeks Reporting Period (Safety Population) |

List of Listings

| Listing Number | Listing Title |
|-------------------|--|
| 16.2.1.1 | Listing of Patient Disposition (All Enrolled Population) |
| 16.2.1.2 | Listing of Subjects with Inclusion, Exclusion and Induction Phase Criteria Deviations (Safety Population) |
| 16.2.2.1 | Listing of Important Protocol Deviations (Safety Population) |
| 16.2.2.2 | Listing of Non-Important Protocol Deviations Related to COVID-19 Pandemic (Safety Population) |
| 16.2.2.3 | Listing of Visits Impacted by COVID-19 Pandemic (Safety Population) |
| 16.2.4 | Listing of Demographic Characteristics (Safety Population) |
| 16.2.5.1 | Listing of Study Drug Exposure (Safety Population) |
| 16.2.5.2 | Listing of Asthma and Exacerbation History (Safety Population) |
| 16.2.5.3 | Listing of Concomitant Medication (Safety Population) |
| 16.2.6.1 | Listing of Oral Corticosteroid Therapy by Treatment Period (Safety Population) |
| 16.2.6.2 | Listing of Exacerbations (Safety Population) |
| 16.2.7.1 | Listing of All Adverse Events (Safety Population) |
| 16.2.7.2 | Listing of Non-Fatal Serious Adverse Events (Safety Population) |
| 16.2.7.3 | Listing of Adverse Events of Special Interest |
| 16.2.7.4 | Listing of COVID-19 Assessments and Symptom Assessments for Subjects with COVID-19 Adverse Events (Safety Population) |
| 16.2.8.1 | Listing of All Laboratory Data for Subjects with any Value Outside of the Normal Range (Safety Population) |
| 16.2.8.2 | Listing of Urinalysis Data (Safety Population) |
| 16.2.8.3 | Listing of Serology Data (Safety Population) |
| 16.2.8.4 | Listing of Subjects Who Became Pregnant During the Study (Safety Population) |
| 16.2.8.5 | Listing of Immunogenicity Results (Safety Population) |

| 16.2.9 | Listing of Electrocardiogram Findings for Abnormal Interpretations (Safety Population) |
|----------|--|
| 16.2.3.1 | Listing of Reasons for Considering as a Serious Adverse Event (Safety Population) |

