5.5. Screen Failures

Participants will be assigned a study number at the time of signing the consent. Participants who do not progress to the screening visit (Visit 1) will be deemed a Prescreen Failure. No data will be captured in the eCRF for these participants.

Those participants that complete at least one additional procedure at Visit 1 (screening) but do not enter the Screening Period (between Visit 1 and Visit 2) will be designated as screen failures. Additionally, those participants that enter the Screening Period, but do not complete any Visit 2 procedures will be designated as run-in failures.

A minimal set of screening information is required to ensure transparent reporting of screen failure participants to meet the Consolidated Standards of Reporting Trials (CONSORT) publishing requirements and to respond to queries from regulatory authorities. Minimal information includes demography, screen failure details, eligibility criteria, and any serious adverse events (SAEs).

Re-screening of participants will be allowed only upon approval by the medical monitor. If a patient is approved to be re-screened the patient would be required to repeat the screening process again from the start of the time and events table, including screening visit and would be assigned a new subject number.

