8.3.1. Time Period and Frequency for Collecting AE and SAE Information

- All SAEs will be collected from the start of intervention until the end of study visit at the time points specified in the SoA (Section 1.3). However, any SAEs assessed as related to study participation (e.g., study intervention, protocol-mandated procedures, invasive tests, or change in existing therapy) will be recorded from the time a participant consents to participate in the study.
- All AEs will be collected from the start of intervention until the end of study visit at the time points specified in the SoA (Section 1.3).
- Medical occurrences that begin before the start of study intervention but after obtaining informed consent will be recorded on the Medical History/Current Medical Conditions section of the case report form (CRF) not the AE section.
- All Initial SAEs will be recorded and reported to the sponsor or designee immediately and under no circumstance should this exceed 24 hours of occurrence, as indicated in Appendix 3. The investigator will submit any updated SAE data /follow-up information to the sponsor within 24 hours of site awareness.
- Investigators are not obligated to actively seek AEs or SAEs after the conclusion of the study participation. However, if the investigator learns of any SAE, including a death, at any time after a participant has been discharged from the study, and he/she considers the event to be reasonably related to the study intervention or study participation, the investigator must promptly notify the sponsor.

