6.1. ALL ENROLLED POPULATION

All participants enrolled and for whom a participant number exists on the study database. This population will be used for summarizing reasons for screen and run-in failures.

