6.2. SAFETY POPULATION

All participants who take at least 1 dose of study intervention. This population will be used for all safety, efficacy and health outcomes.

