11.2. Adverse Events

The applicable definition of an Adverse Event (AE) is in the study protocol Sections 8.3 and 10.3. All AEs occurring from when a subject sign informed consent to when a subject exits the study will be accounted for in the reporting. AEs occurring pre-treatment, on-treatment and post-treatment periods will be summarized for the safety population.

A pre-treatment AE is defined as any AE with an onset date before the date of first exposure to the study drug. An on-treatment-AE is an event does not present prior to first exposure to the study drug or any pre-existing event that worsens following exposure to study drug until the last exposure to the study drug plus 28 days inclusive. Any AE which occurs after 28 days of last exposure to the study drug will be considered as post-treatment AEs. All AEs will be coded using the MedDRA central coding dictionary (26.0) and grouped by body system and preferred term. See Appendix 1 for imputation of partial dates for AEs. Imputed dates will be used to determine on-treatment status.

The following summaries will be generated for adverse events:

- AEs by treatment period (on and post-treatment), SOC and PT
- Common (>=3%) non-serious on-treatment AEs by SOC and PT

- AE occurred on the day of dosing by SOC and PT
- On-treatment drug-related AEs by SOC and PT
- AEs leading to permanent discontinuation or withdrawal from study by SOC and PT
- Serious AEs by treatment period (pre, on and post-treatment), SOC and PT
- Non-fatal SAE by treatment period (pre, on and post-treatment), SOC and PT
- Fatal SAE by treatment period (on and post-treatment), SOC and PT

Events with missing relationship to the study drug is considered as related. In addition, a summary of overall AEs during the study duration will be presented which includes:

- Subjects with at least one AE
- Subjects with at least one drug-related AE
- Subjects with AE leading to premature discontinuation
- Subjects with at least one serious AE
- Subjects with at least one drug-related serious AE
- Subjects with at least one AE leading to death
- Any on-treatment AEs
- Any on-treatment SAEs

The following listings will be generated:

- Listing of all Adverse Events
- Listing of Fatal Adverse Events
- Listing of Non-Fatal Serious Adverse Events
- Listing of Adverse Events Leading to Discontinuation of Investigational Product and/or Withdrawal from the Study

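### SAEs and deaths in participants who reach Visit 1 but are never dosed have no planned SAE or death table or listing, although SAP 11.2 undertakes to account for events from consent onward

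*SAP*

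**What the plan says.** **Collection.** Protocol 8.3.1 starts general AE and SAE collection at the first dose, but SAEs judged related to study participation "will be recorded from the time a participant consents to participate in the study". Other medical events between consent and first dose go to medical history, so before dosing the point concerns SAEs only. Protocol 5.5 sets a minimum data set for screen failures: "Minimal information includes demography, screen failure details, eligibility criteria, and any serious adverse events (SAEs").

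**Reporting statement.** SAP 11.2: "All AEs occurring from when a subject sign informed consent to when a subject exits the study will be accounted for in the reporting".

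**Population actually used.** The next sentence of SAP 11.2 limits the pre-, on- and post-treatment summaries to the Safety Population, and the opening of SAP Section 11 applies that population to the whole section. SAP 6.2 defines it as "All participants who take at least 1 dose of study intervention". Of the All Enrolled Population, SAP 6.1 says: "This population will be used for summarizing reasons for screen and run-in failures".

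**Output list (SAP Appendix 5).**
- Table 14.3.2.1: "Summary of Serious Adverse Events by Treatment Period (Pre, On and Post-Treatment), System Organ Class and Preferred Term (Safety Population"). Table 14.3.2.2, on non-fatal SAEs, has the same periods and population.
- Table 14.3.2.3: "Summary of All Fatal Adverse Events by Treatment Period (On and Post-treatment), System Organ Class and Preferred Term (Safety Population").
- Listing 16.2.7.2: "Listing of Non-Fatal Serious Adverse Events (Safety Population"). Listings 16.2.7.1 (all AEs) and 16.2.3.1 (reasons for seriousness) carry the same label.
- The listing of fatal AEs named in SAP 11.2 does not appear in Appendix 5.

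**The concern.** The protocol asks sites to record SAEs in people who are then never dosed, and the SAP says events from consent will be reported, but no SAE or death output is planned on a population that contains those people. The SAP also chose to show a pre-treatment period in Tables 14.3.2.1 and 14.3.2.2. Restricted to people who went on to be dosed, those columns leave out exactly the SAEs that stopped someone from being dosed. Inclusion then depends on the outcome of the event itself.

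At stake is complete safety reporting in a study whose primary objective is safety. Participants undergo protocol procedures before dosing, including withholding bronchodilators before spirometry and maximum post-bronchodilator testing at Visit 1. Protocol 5.5 gives transparent reporting and regulators' queries as the reasons for collecting these data.

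**Working it through.** **1. Where a pre-dose SAE would be reported, by type of participant**

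| Participant | Pre-dose SAE collected? | Planned SAE or death table or listing? |
|---|---|---|
| Consented, never reached Visit 1 | No eCRF data (Protocol 5.5) | None; nothing to report |
| Reached Visit 1, never dosed | Study-related SAEs (8.3.1); any SAE for screen failures (5.5) | None |
| Reached Visit 1, later dosed | Study-related SAEs (8.3.1) | Pre-treatment columns of Tables 14.3.2.1 and 14.3.2.2; Listings 16.2.7.1 and 16.2.7.2 |

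The gap is the middle row. It follows from the population definition alone: no dose means not in the Safety Population, and every SAE or death output is on that population, either by its Appendix 5 label or, where no label is given, by the rule at the head of SAP Section 11. The outputs without a label are Listing 16.2.7.3 (AESIs) and the missing fatal-AE listing.

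**2. What the All Enrolled Population is used for.** It carries disposition (Table 14.1.1.1, Listing 16.2.1.1) and failure reasons (Table 14.1.1.3). None of these is an SAE output.

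**3. How many participants fall in the middle row.** Inputs are from Protocol 9.2 and SAP 5.3: 100 on treatment and a 35% screen failure rate.
- The plan's own figure: 100 / (1 − 0.35) = 153.8, rounded up to 154. It reproduces.
- Undosed: 154 − 100 = 54, taking screened to mean reached Visit 1. Rescreened participants get a new number (Protocol 5.5), so 54 records may be fewer than 54 people.

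**4. How long they are observed.** Screening lasts at most about two weeks (Protocol 1.1).
- Undosed: at most 54 × 2 = 108 person-weeks. Those who fail at Visit 1 contribute almost nothing.
- Dosed: 100 × 24 = 2,400 person-weeks on treatment, plus at most 100 × 2 = 200 before dosing.
- Share of observed time: 108 / (108 + 2,400 + 200) = 108 / 2,708 = 4.0%.

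**5. How many events that could be.** The documents give no pre-dose SAE rate. For an assumed per-person risk p, the expected number is 54p and the chance of at least one event is 1 − (1 − p)^54.

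| Assumed p | Expected SAEs | Chance of at least one |
|---|---|---|
| 0.1% | 0.05 | 5.3% |
| 0.5% | 0.27 | 23.7% |
| 1% | 0.54 | 41.9% |
| 2% | 1.08 | 66.4% |

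Over this assumed range, about one event or none is expected.

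**The case against.** **The event need not vanish.** Protocol 9.4.1 plans narratives for deaths and SAEs, and its sentence does not exclude undosed participants, although the section opens by restricting safety analyses to the Safety Population. A death or SAE could also appear as a reason in Table 14.1.1.3 or Listing 16.2.1.1. Oversight does not rest on these tables, because SAEs go to the sponsor within 24 hours and to the regulator. All of this stands. None of it gives a count or a listed SAE record, which is what the statement in SAP 11.2 implies.

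**The population choice is the protocol's own.** Protocol 9.3 and 9.4.1 put all safety analyses on dosed participants, and the SAP follows. That is right for the on- and post-treatment tables. But the SAP adds its own statement about events from consent, and its introduction lets it supersede the protocol, so the mismatch can be settled there.

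**The fatal-AE table needs no pre-treatment column.** In a table of dosed people that column would be empty. This is a consequence of the population, not a second defect.

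**Two stronger readings a reader might infer.** One is that 35% of the safety information is lost. The ratio 54/154 is a share of planned participants, not of events or time. On time the ceiling is about 4%, and no event share can be derived. The other is that the pre-treatment columns will make the period before dosing look safer than treatment. No such comparison is planned, there is no hypothesis testing, and the periods differ in length (one to two weeks against 24 weeks).

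**Conclusion.** The point holds as a gap in completeness of reporting. Followed as written, the SAP gives a collected SAE or death in a participant who reached Visit 1 and was never dosed no place in any SAE or death table or listing, which contradicts its own statement in 11.2. The pre-treatment columns of Tables 14.3.2.1 and 14.3.2.2 omit any SAE that prevented dosing.

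The size is limited. The primary estimand counts events from first dose to 28 days after last dose and does not change. The number of affected events is unknown and probably small. The conclusion rests on two readings: that the Section 11 rule governs the outputs with no population label, and that sites collect SAEs in undosed participants as Protocol 8.3.1 and 5.5 require. Those two sections differ in scope, study-related SAEs in one and any SAE for screen failures in the other, so what the pre-dose data will contain is itself not settled.

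**What to change.** - In SAP 11.2 and Appendix 5, run Listing 16.2.7.2 on the All Enrolled Population. Add the missing fatal-AE listing on the same population. In both, flag participants who were never dosed.
- Base the flag on the absence of a first dose, not on the failure category. Under Protocol 5.5, someone who completes a Visit 2 procedure and is then not dosed is neither a screen failure nor a run-in failure. Link rescreened participants across their subject numbers.
- Add one count of SAEs and deaths in enrolled but undosed participants, for example as a separately labelled line under Table 14.3.2.1, outside its denominators.
- Extend the stated use of the All Enrolled Population in SAP 6.1 to cover these outputs. Keep the Safety Population for the on- and post-treatment tables.
- Reconcile Protocol 8.3.1 with 5.5 on which SAEs are collected before dosing. Only then add any footnote on pre-treatment ascertainment. A footnote saying that only study-related SAEs are collected would conflict with 5.5 for screen failures.

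Cost: SAP wording, one population filter and a few more listing lines. The protocol already calls for the data and the population is already defined.
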